Feasibility Study to Improve Atrial Fibrillation Outcomes Using a Digital Application for Cardiovascular Risk Reduction: Precursor to a Multicenter Randomized Trial

Study Protocol and Statistical Analysis Plan

NCT04050982

May 17, 2022

Title Feasibility Study to Improve Atrial Fibrillation Outcomes using a Digital Application for Cardiovascular Risk Reduction: Precursor to a Multicenter Randomized Trial

Purpose

An effective intervention to support cardiovascular risk factor (CVRF) reduction in individuals with AF that can be easily provided with existing resources does not exist, despite the evidence that even though CVRF reduction has been shown to decrease AF symptom severity and burden. The digital application, AF CARE, has been specifically designed to fill this critical need to support CVRF reduction in individuals with AF, and can be easily incorporated into the care delivered to individuals undergoing AF catheter ablation (CA), but its feasibility is unknown. Demonstrating that an available digital application can improve AF outcomes would be significantly impactful.

The specific aims of this study are to: 1). Test the feasibility of AF CARE in terms of acceptability, demand, usage, adherence, and integration (1), and 2). Determine the efficacy of AF CARE based on the pre-post assessment of CVRF (LS7 and/or blood tests), AF knowledge, AF Symptom Severity and Burden (AFSS), and QOL assessment at baseline, 3, and 6 months in the AF CARE group compared to the usual care (UC) group to provide estimates of effect size.

Background and Significance

Atrial fibrillation (AF) is the most common cardiac arrhythmia disorder in the United States, contributing to a five-time greater risk of stroke and is independently associated with increased mortality (2,3). Predictions of doubling the AF population is based on aging and increased prevalence of cardiovascular risk factors (4). A predicted lifetime risk of AF rises from 20% to 33% with the addition of a single elevated CVRF (4,5,6). Innovative interventions that promote the reduction of CVRF are needed to decrease AF symptom severity and burden.

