Current AF treatment guidelines include CVRF reduction, and when reduced in a randomized group, particularly weight loss, there was a significant reduction in AF burden and AF symptoms compared to those who received usual care (7,8). A maintained weight loss of at least 10% contributed to the greatest reduction in AF symptoms and AF burden (9). While AF CA procedures significantly reduce AF symptom burden (10) and decrease AF associated mortality and morbidity (11), recurrences resulting in increased morbidity and mortality persist (12). Altering the disease substrate with CVRF reduction and modifying the electrical substrate with CA procedures has shown an improvement in post-AF ablation outcomes, with less AF symptom severity/burden (13,14).

Lifestyle modifications to reduce CVRFs are difficult. There is no consensus on which intervention for CVRF reduction is most effective (15), nor what delivery mode is most acceptable. The American Heart Association (AHA) Center for Health Technology and Innovation collaborated with the Stanford Center for Digital Health and PatientBond, a digital technology software company, to design a personalized digital application (app) that can be accessed via a smartphone, iPad, or personal computer (16). This digital app, AF CARE, delivers patient-specific messages to promote behaviors that will reduce

CVRF and improve AF knowledge, based on each individual's responses to 12 psychographic questions, 12 AHA Life's Simple 7 (LS7) questions, and specific biometrics. To date, the utility and effectiveness of AF CARE to reduce CVRF has not been tested.

Research Design

Phase I will be completed prior to randomization on 10 individuals with AF who will be asked to participate in interface testing of the digital platform for 1-3 months to identify potential programming modifications to enhance usage and adherence.

Then, the primary aim of Phase II of this study will be to determine feasibility of utilizing AF CARE to provide lifestyle modification support to patients with AF. The secondary outcome will be to compare the CVRF, AF knowledge, AF Symptom Severity and Burden, and QOL between and within the UC group and the CARE AF group. This feasibility study will use a prospective, RCT wait list design to allow for the determination of effect sizes to inform the power calculation for a multi-center trial, if found to be effective. (Phase I).

a. Sample: Sixty patients undergoing treatment for AF at Stanford Health Care.

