Inclusion: ≥ 18 years old, $\text{BMI} \geq 28 \text{ kg/m}^2$ AND one additional CVRF, access and willingness to engage in digital technology, has a valid email address and a cell phone number, and able to ambulate and speak/read English

Exclusion: Class III/IV heart failure, MI or cardiac surgery in prior 3 months, severe renal/hepatic disease, active malignancy, current/recent (within 6 months) enrollment in weight loss program.

b. Participants will be recruited when they are being followed for the management of their atrial fibrillation in the Stanford clinic.

c. Procedure: Individuals meeting inclusion criteria, but not excluded, will be invited to participate. Once consented, demographics, biometrics and baseline measures will be collected. Both groups will be asked to enter initial responses into AF CARE and then will be randomized to either the digital platform AF CARE group and UC or Wait List Group. The UC wait list group will receive usual care for the first 3 months and then they will receive the digital platform (AF CARE) after 3 months of enrollment. Both groups will be appropriately referred for smoking cessation, behavioral medicine, endocrinology, and/or sleep clinic during initial and Month 3 visit, based on screening completed at that visit. Initial measures will be collected, and repeated at Month 3, Month 6, and Month 12.

Both AF CARE/UC and Wait List Groups	Initial	Month 3 (CA)	Month 6	Month 12
Medical History and Physical	X	X	X	X
Demographics	X			
Psychographic score	X			
AHA Life's Simple 7	X	X	X	X
Biometrics- pt reported (BP, HR, RR, waist, BMI)	X	X	X	X
Blood testing, if available: Lipid panel, Blood Sugar	X		X	X
6 Minute Walk Test	X	X	X	X
Jessa AF Knowledge Questionnaire	X	X	X	X
AF Symptom Severity Scale (AFSS)	X	X	X	X

Ambulatory Monitor (Zio patch)- if available	X	X	X	X
AF Effect on Quality of Life (AFEQT)	X	X	X	X
AF CARE Group -Access to AF CARE	X-----→			
Wait List Access to AF CARE	X-----→			

AF CARE GROUP: Patients will receive personalized messages twice weekly that will include behavior recommendations for CVRF reduction and AF education from the AHA library. Messages will be patient-specific based on the initially entered psychographic profile and data entered.

Ongoing messages will include participant response requests and future messages elicited by AF CARE will be based on entered responses.

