During the protocol, 3 participant non-responses to communications will result in a message being sent to the research team to prompt a call to the participant to enforce the importance of the messaging. In addition, a participant posting a negative response (e.g. "I do not know how to get my medicine refilled") will also result in a message being sent to the research team to determine if clinical follow-up is required.

Wait List UC Group/AF CARE Group: Participants will be given a weight loss goal of 10% and other recommendations for CVRF reduction based on their initial LS7 assessment. They will be provided written educational materials to review independently on AF and AF CA treatment.

Participants in this group will receive personalized messages twice weekly that will include behavior recommendations for CVRF reduction and AF education from the AHA library starting at 3 months following randomization. Measurable Outcomes: (See Table above).

- a. CVRF will be evaluated using the pre-post measures of the AHA Life's Simple 7, along with patient reported blood pressure, BMI, blood tests (lipids and glucose), and 6-minute walk test.
- b. AF knowledge will be evaluated with the Jessa AF Knowledge Questionnaire
- c. AF Symptom Severity and Burden will be measured with the AF Symptom Severity Scale
- d. QOL will be measured with the AF Effect on Quality of Life Questionnaire, and the Patient Health Questionnaire-9

Data Analysis: Demographic data will be analyzed using descriptive statistics for continuous data and frequencies and percentages for categorical data.

The feasibility of AF CARE will be determined by calculating acceptability, demand, AF CARE usage, adherence, and qualitative interview data analysis.

Efficacy will be evaluated on CVRF, AF Knowledge, AF symptom severity and burden, and QOL using matched pair t-tests at baseline, 3 and 6, and 15 months to determine the differences between and within groups. This data will be used to calculate the sample size required in a future multicenter trial designed to achieve 80% power to detect a change of 10% from baseline.

- d. Potential Pitfalls: Data integrity is an issue for self-reported measures in the usual care group. The level of usage with the AF CARE plan may be suboptimal or AF CARE may be ineffective in meeting study aims.

e. Sustainability: Sustainability will be determined by participant engagement and efficacy.

References

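### Within-arm change is tested as efficacy, but in each arm the app starts together with a referral round, so only the Month 3 between-arm difference isolates AF CARE

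*Combined protocol and SAP*

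**What the plan says.** **Referrals.** Research Design, item c (Procedure): "Both groups will be appropriately referred for smoking cessation, behavioral medicine, endocrinology, and/or sleep clinic during initial and Month 3 visit". The sentence adds that this is "based on screening completed at that visit", so referral is conditional.

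**Timing of the app.** The AF CARE arm has the app from the start. The wait-list arm has usual care for three months and then receives the app. The Month 3 column of the schedule also carries the label CA, the protocol's abbreviation for catheter ablation.

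**Efficacy aim.** Purpose, Aim 2: "Determine the efficacy of AF CARE based on the pre-post assessment of CVRF (LS7 and/or blood tests), AF knowledge", followed by symptom and quality-of-life measures at baseline, 3 and 6 months, "in the AF CARE group compared to the usual care (UC) group to provide estimates of effect size".

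**Analysis.** Research Design gives the secondary outcome as a comparison of risk factors, knowledge, symptoms and "QOL between and within the UC group and the CARE AF group". Data Analysis evaluates efficacy with matched-pair t-tests "to determine the differences between and within groups" and names no other test. It then says the data will be used to size a multicenter trial with 80% power for a 10% change from baseline.

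**Entry.** Participants need a BMI of at least 28 "AND one additional CVRF".

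**The concern.** The referral services plausibly act on the risk-factor outcomes the trial measures: smoking within Life's Simple 7, blood pressure, BMI and glucose. If a referral round and the app begin at the same visit, improvement from that visit onwards belongs to both, and nothing in the analysis plan divides it. An app with no effect could therefore show a significant within-arm improvement in an analysis that the plan places under efficacy.

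Two features of Data Analysis pull towards that reading. The only named test is a paired one, which suits change within a person and not a comparison of two independent randomized groups. The target for the next trial is a change from baseline, not a difference between arms.

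At stake is the study's stated use: effect sizes for a multicenter trial, to follow if the app proves effective. An estimate that contains shared gains could favour going ahead and make the next trial too small.

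**Working it through.** There is no figure in the plan to reproduce. The sample of 60 comes without an alpha, SD, effect or power, and the 80% power and 10% change belong to a future trial with no sample size given. The check is therefore structural, followed by an illustration.

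**1. What starts when** (Procedure and schedule table)

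| Interval | AF CARE arm | Wait-list arm |
|---|---|---|
| Initial to Month 3 | app starts; Initial referral round | no app; Initial referral round |
| From Month 3 | app continues; Month 3 referral round | app starts; Month 3 referral round |

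Read down either column, the app never starts alone. Read across the first row, the arms differ in the app while the referral offer is the same. After Month 3 both arms have the app, so no app-free control remains.

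**2. What each contrast estimates.** Let A be the app's effect on the Initial-to-Month 3 change, and C the mean change from everything shared (referrals, time trend, regression to the mean, and ablation if it falls in the interval). Assume the two add.
- Within the AF CARE arm: expected change = A + C.
- Within the wait-list arm over the same interval: expected change = C.
- Between arms: (A + C) − C = A.
- Within the wait-list arm after Month 3: the app's effect plus a new shared term, again inseparable.

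**3. Illustration of size.** Assumptions, none given in the documents: 1:1 allocation, so 60/2 = 30 per arm; two-sided 5% tests; A = 0; shared gain of c SDs of the change score in both arms. The paired test statistic then follows a noncentral t with 29 degrees of freedom and noncentrality c√30.

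| c | c√30 | Paired test significant in the AF CARE arm |
|---|---|---|
| 0 | 0 | 5% |
| 0.125 | 0.68 | 10% |
| 0.25 | 1.37 | 26% |
| 0.3 | 1.64 | 36% |
| 0.5 | 2.74 | 75% |

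The rows 0.125 and 0.25 correspond to a quarter or a half of the arm gaining 0.5 SD (0.25 × 0.5 and 0.5 × 0.5), ignoring the added spread. With 24 completers per arm, the figures at 0.3 and 0.5 are 29% and 65%.

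A two-sample t-test on change scores, simulated 40,000 times at each of c = 0, 0.2, 0.3, 0.5 and 0.8, was significant in 4.8% to 5.1% of trials, because c cancels.

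**4. Precision of the between-arm contrast.** By the normal approximation, the difference detectable with 80% power is (1.960 + 0.842) × √(2/30) = 0.72 SD. Power at 0.5 SD is 49%.

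**5. Outcomes available at Month 3.** The schedule marks lipids and blood sugar at Initial, Month 6 and Month 12 only. Laboratory lipids and glucose therefore have no measurement while one arm has the app and the other does not.

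**The case against.** The strongest reply is that the right comparison is already planned. Aim 2 does not stop at pre-post assessment: it sets AF CARE against usual care and ties the effect size to that comparison, and Data Analysis lists between-group differences too. A reader might infer that efficacy rests on within-arm change alone. The documents do not support that. What remains is that within-group tests also stand under efficacy, with no descriptive label, and that no test suited to the between-arm comparison is named.

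A reader might also infer that the referrals are themselves a design fault, or that everyone receives them. Neither follows. Referral depends on screening, and offering the same referrals to both arms protects the randomized contrast, since their effect cancels in expectation at Month 3. Month 3 referrals can affect only later results.

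Three further limits stand in full:
- The plan has no success rule. It does not say that a within-arm p-value would establish efficacy, so it cannot be said that a false claim would be made, only that the text leaves room for one.
- The percentages rest on an assumed shared gain. They are not estimates for this trial.
- Regression to the mean concerns mainly BMI and the other risk factors used for entry. AF knowledge, AF symptoms and quality of life are not entry criteria.

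The ablation point is also only a possibility, because the text does not say who has ablation at Month 3.

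**Conclusion.** The concern holds as a matter of analysis and labelling. No within-arm change in this design isolates the app, yet such change is tested under efficacy, and the future trial's target is worded as change from baseline. The between-arm difference at Month 3 is free of the shared gain in expectation, provided the arms are referred alike and shared gains add to the app's effect.

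The direction is clear if shared gains are improvements: within-arm results flatter the app. The size cannot be fixed from the documents. Feasibility is the primary aim of Phase II and these comparisons are secondary, so this should be corrected but does not undermine the study's main purpose.

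**What to change.** - In Aim 2 and Data Analysis, define AF CARE efficacy, and the effect size carried to the future trial, as the between-arm difference at Month 3.
- Estimate it with an independent-groups method adjusted for baseline, such as ANCOVA, and report a confidence interval. Drop the matched-pair test for this comparison.
- Label all within-arm changes, and all results after Month 3, as descriptive.
- Express the future trial's target as a between-arm difference.
- Record referrals made, by arm, at the existing visits. The plan does not say whether Initial referrals precede randomization, so any imbalance should be visible.
- State that laboratory lipids and glucose have no concurrent app-versus-no-app estimate under the present schedule.

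**Cost.** Wording in two sections and one data field at existing visits. Within-arm p-values would no longer support efficacy. The between-arm estimate will be imprecise: with 30 per arm, 80% power needs about 0.72 SD of the change score. Baseline adjustment may improve on this, by an amount that depends on correlations the plan does not give. Laboratory lipids and glucose would have descriptive results only.

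### The schedule leaves lipids and glucose unmarked at Month 3, the only visit after baseline at which they could be compared between AF CARE and usual care

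*Combined protocol and SAP*

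**What the plan says.** All references are to the combined protocol and SAP.

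- **Purpose, aim 2.** Efficacy rests on the "pre-post assessment of CVRF (LS7 and/or blood tests") together with knowledge, symptom and quality-of-life measures, "at baseline, 3, and 6 months in the AF CARE group compared to the usual care (UC) group". The stated use is to estimate effect sizes.
- **Research Design, item c (Procedure).** "Initial measures will be collected, and repeated at Month 3, Month 6, and Month 12". No exception for blood tests is written. On the control arm: "The UC wait list group will receive usual care for the first 3 months", after which it receives AF CARE. The description of the wait-list group agrees, with its messages "starting at 3 months following randomization".
- **Schedule table.** "Blood testing, if available: Lipid panel, Blood Sugar" is marked at Initial, Month 6 and Month 12, with an empty Month 3 cell. The row "Ambulatory Monitor (Zio patch)- if available" carries the same condition and is marked at all four visits.
- **Measurable Outcomes, item a, and Data Analysis.** Lipids and glucose are listed among the CVRF measures, with no and/or. CVRF is then analysed between and within groups at time points that include 3 months. The heading of the outcome list refers the reader back to the schedule table.

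**The concern.** In a wait-list design, the arms differ in the way aim 2 requires only until the wait-list arm starts the intervention. Here that is 3 months, so Month 3 is the one post-baseline visit at which a between-arm difference estimates AF CARE against usual care. The schedule omits lipids and glucose at that visit alone, while the surrounding text suggests that they are measured and analysed there.

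If the table is followed, the Month 6 and Month 12 between-arm differences in lipids and glucose answer a different question: immediate against delayed access. If they were reported under aim 2 as effects against usual care, they could understate the effect by an amount that the trial cannot show.

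**Working it through.** The plan gives no figure on this point to reproduce. The check compares the passages, counts exposure and gives a short illustration.

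**1. Is the blank isolated?** The repeated rows other than blood testing are history and physical, LS7, biometrics, 6-minute walk test, Jessa knowledge questionnaire, AFSS, ambulatory monitor and AFEQT. All 8 of 8 are marked at Month 3. The ambulatory monitor is also collected only if available, so optional status does not explain the blank.

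**2. Months of AF CARE access at each visit** (visit month for the AF CARE arm; visit month minus 3, not below 0, for the wait-list arm):

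| Visit | AF CARE arm | Wait-list arm | Blood test marked |
|---|---|---|---|
| Initial | 0 | 0 | yes |
| Month 3 | 3 | 0 | no |
| Month 6 | 6 | 3 | yes |
| Month 12 | 12 | 9 | yes |

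Of the 2 post-baseline blood tests, 0 fall before wait-list access.

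**3. What the later contrasts would show.** Let E(t) be the effect after t months of access. Assume that it depends only on t, does not reverse, is the same in both arms, and that access continues. The share of the effect against usual care that the between-arm difference retains is [E(6) − E(3)]/E(6) at Month 6 and [E(12) − E(9)]/E(12) at Month 12.

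| Assumed accrual | Month 6 | Month 12 |
|---|---|---|
| Plateau by 3 months | 0 | 0 |
| Linear | 3/6 = 50% | 3/12 = 25% |
| None before 3 months, then linear | 3/3 = 100% | (9 − 6)/9 = 33% |

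The plan does not say which curve applies. The table shows only that the later contrasts have no fixed relation to the effect that aim 2 asks for.

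**4. Precision of an added Month 3 comparison.** The 95% half-width in SD units is t(0.975, 2n − 2) × √(2/n), with n tested per arm. The sample is 60; the 1:1 split is an assumption, because no allocation ratio is stated.

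- n = 30: 0.52
- n = 15: 0.75
- n = 10: 0.94

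The number who will have values is unknown, so these span a range.

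**The case against.** **The texts can be read together.** Aim 2 says LS7 and/or blood tests, so LS7 at Month 3 satisfies it. The sentence on repeated measures is general: demographics and the psychographic score are not repeated either. The outcome list points back to the table, so the list may name the CVRF components and the table may set their timing. This stands. A reader might infer that the schedule flatly contradicts each of these passages; the wording does not support that. What remains is an exception that is neither stated nor explained. The reading also leaves the exposure count unchanged.

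**Month 3 need not show a larger effect.** Under the same three curves, E(3)/E(6) is 100%, 50% and 0%, the mirror image of the Month 6 shares. That is correct, and the case for Month 3 is not one of power. Month 3 is the only visit at which the difference estimates AF CARE against usual care at all.

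**The stake is small, and not specific to blood.** The tests are optional and secondary, Phase II is primarily about feasibility, and every between-arm comparison after Month 3 is immediate against delayed access. All of this stands. The other CVRF measures, however, have a controlled Month 3 comparison, and lipids and glucose have none.

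**The table may be damaged.** The row "Wait List Access to AF CARE" appears to start under Initial, from which a reader might infer that the wait-list arm has access from the outset. Two explicit statements in the text put it at 3 months, and the row is probably displaced by PDF extraction. The blood row's blank lies between two marks, so a simple column shift does not explain it; it should still be confirmed in the PDF.

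**Conclusion.** The point holds as an unreconciled inconsistency with a definite consequence. Under the table, none of the 2 post-baseline blood comparisons is AF CARE against usual care, so the trial as scheduled gives no lipid or glucose effect size against usual care. This rests on the text's 3-month start of wait-list access and on the table cell being blank as extracted. It does not rest on any assumed accrual curve.

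The scope is limited to optional, secondary measures. Two wider conclusions are not supported. A reader might infer that the CVRF outcome as a whole has no controlled comparison; LS7, biometrics and the 6-minute walk test all have one at Month 3. A reader might also infer that the next trial would be wrongly sized; Data Analysis sizes it on a 10% change from baseline, and nothing makes lipids or glucose the driver. Within-group blood analyses at the scheduled visits are unaffected. The change should be made, but the feasibility aim does not depend on it.

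**What to change.** Add a Month 3 mark to the blood-testing row. Record in both arms the lipid and glucose values available near that visit and before the wait-list arm starts AF CARE. Keep the Month 6 and Month 12 marks. This brings the table into line with aim 2, the sentence on repeated measures and the 3-month CVRF analysis. It costs one table cell and a little more data collection. It requires no added procedure, since only available values are recorded, but it guarantees no data, and the estimate should be reported with its interval because it will be imprecise.

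If the omission is deliberate, state that blood tests are excepted at Month 3 and that lipids and glucose have no 3-month analysis. Label the Month 6 and Month 12 between-arm blood comparisons as immediate versus delayed AF CARE, and do not report them as effects against usual care. On either route, the same label belongs on every between-arm comparison after Month 3. The relabelling costs nothing.

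### Blood lipids and glucose are optional and the risk factor outcome is defined in two ways, so within-group paired tests on blood values could show improvement without a treatment effect

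*Combined protocol and SAP*

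**What the plan says.** - **Collection.** The schedule table under c. Procedure has the row "Blood testing, if available: Lipid panel, Blood Sugar". It is marked at Initial, Month 6 and Month 12, and the Month 3 cell is blank. The text above the table says that the initial measures are repeated at Month 3, Month 6 and Month 12. LS7 is marked at all four visits without the availability qualifier.
- **Outcome, first definition.** Specific aim 2 (Purpose) bases efficacy on "pre-post assessment of CVRF (LS7 and/or blood tests" and other measures, at baseline, 3 and 6 months, against usual care.
- **Outcome, second definition.** Measurable Outcomes, item a, evaluates risk factors by LS7 "along with patient reported blood pressure, BMI, blood tests (lipids and glucose), and 6-minute walk test".
- **Analysis.** Data Analysis evaluates efficacy "using matched pair t-tests at baseline, 3 and 6, and 15 months to determine the differences between and within groups". The results are to size a later trial "designed to achieve 80% power to detect a change of 10% from baseline".
- **Design.** The sample is "Sixty patients undergoing treatment for AF at Stanford Health Care", randomized with a wait list. For wait list participants, "they will receive the digital platform (AF CARE) after 3 months of enrollment".

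The documents do not say what makes a blood test available, who orders it, what time window applies, what happens when one of a pair is missing, or which risk factor component decides the result.

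**The concern.** A matched-pair test uses only participants with both values. When the second value is optional, those with pairs may differ from the rest. If a high first value makes a second test more likely, the pairs are chosen partly for a chance high, and their mean falls at retest without any effect of the app. A within-group t-test would count that fall as efficacy, and it could then be carried into planning the multicenter trial.

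The two outcome definitions are a separate weakness. One allows LS7, blood tests, or both; the other lists five kinds of measure together; neither names the one that decides. The risk factor result can then be chosen after the data are seen, and under the first definition it can differ between participants with and without blood results.

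**Working it through.** The plan gives no figure to reproduce: the sample of 60 has no derivation, and the 80% power and 10% change belong to the future trial. The questions are how large the artefact could be, and which blood comparisons the schedule allows.

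**1. Which blood comparisons exist.** Data Analysis names follow-up tests at 3, 6 and 15 months. Month 3 has no blood mark and Month 15 is not in the schedule, so only Month 6 has both a planned test and a scheduled blood value. The wait list group receives AF CARE after 3 months, so at Month 6 and Month 12 both arms have had access to it. No scheduled blood comparison is against a control group without AF CARE.

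**2. Size under all-or-nothing selection.** Assume normal values with standard deviation SD, test-retest correlation r, no treatment effect, and retesting only above the baseline mean.

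Expected change = −(1 − r) × SD × φ(0) / (1 − Φ(0)), where φ(0)/(1 − Φ(0)) = 0.399/0.5 = 0.798.

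- r = 0.8: 0.2 × 0.798 = a fall of 0.16 SD
- r = 0.6: 0.4 × 0.798 = a fall of 0.32 SD

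With an assumed coefficient of variation of 0.20 to 0.30, this is 0.16 × 0.20 = 3.2% to 0.32 × 0.30 = 9.6% of the mean. The planning target is a 10% change.

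**3. Weaker selection.** If three-quarters of those retested lie above the mean, drawn at random within each half, their baseline mean is 0.75 × 0.798 − 0.25 × 0.798 = 0.40 SD above average. The fall is then 0.2 × 0.40 = 0.08 SD to 0.4 × 0.40 = 0.16 SD.

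**4. Graded selection, by simulation.** There is no true effect, 30 per arm (assumed, since no allocation ratio is given), and retest probability 1/(1 + exp(−b × z)) for baseline z-score z. This gives about 15 pairs per arm. There were 6,000 repetitions and two-sided 5% tests; ranges cover r = 0.6, 0.7 and 0.8. The third column has a nominal value of 2.5%, the fourth 5%.

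| Selection | Mean within-arm change (SD) | Falsely significant within-arm improvement | False between-arm difference |
|---|---|---|---|
| None, b = 0 | about 0 | 2.2–2.6% | 4.6–4.9% |
| b = 1, both arms | −0.08 to −0.17 | 6.5–9.6% | 4.6–5.3% |
| b = 2, both arms | −0.12 to −0.24 | 10.4–17.0% | 4.8–5.3% |

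If selection acts in one arm only, the spurious between-arm difference is 0.08 to 0.25 SD and the between-arm error is 6.5% to 10.8%.

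The correlations, the coefficient of variation and the selection strengths are all assumptions; none comes from the documents.

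**The case against.** A reader might infer that blood tests are ordered in routine care because of abnormal values, so that the pairs are clinically selected. The documents do not say this. The schedule says only that testing depends on availability, and it puts the same qualifier on the ambulatory monitor. The referral sentence under c. Procedure covers both groups and does not mention blood tests. Availability may reflect access or logistics, and if it is unrelated to the first value it adds no regression to the mean. This part of the objection stands, and the bias must be stated as conditional.

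It can also be said that aim 2 is a comparison with usual care, that regression to the mean cancels between arms when selection is equal, that efficacy is secondary to feasibility, and that the future trial's target is already fixed at 10%. The cancellation is correct and the simulation shows it. It does not protect the within-group tests, which Data Analysis plans explicitly. Nor does it supply a blood comparison with usual care, because none is scheduled. As for the fixed target, Research Design says that effect sizes from this study will inform the power calculation, so an inflated change could still be carried forward.

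Finally, the either-or wording is not the only definition of the outcome. That is true, and the defect is that the two definitions disagree.

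**Conclusion.** The point holds in a limited form. Three parts rest on the text alone: blood values are optional with no rule for missing pairs, the risk factor outcome has two conflicting definitions, and no blood value is scheduled while the arms differ in access to AF CARE.

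The regression-to-the-mean part is conditional on retesting being related to the first value. Its size is 0.16 to 0.32 SD only under the extreme assumption of retesting solely above the baseline mean with correlation 0.6 to 0.8. The documents do not support the reading that paired blood changes in this trial are an artefact of selection, or that between-arm blood comparisons are necessarily biased.

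Within-group blood change is weak evidence of efficacy in any case. Entry requires a raised BMI "AND one additional CVRF", which could itself cause some regression to the mean even with complete sampling. The change to the plan is worth making because it closes the choice of outcome whether or not selective retesting occurs.

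**What to change.** 1. In aim 2, Measurable Outcomes item a and Data Analysis, name LS7 as the single risk factor efficacy outcome, compared between arms at Month 3 with adjustment for baseline. State how LS7 is scored and whether any of its items need a blood result, since the documents do not say.
2. List blood pressure, BMI and walk test separately as secondary measures.
3. Make lipids and glucose descriptive. Report by arm the number with paired values, and the baseline values of those with and without pairs.
4. Label any between-arm blood contrast at Month 6 or Month 12 as earlier versus later access to AF CARE.
5. Do not use within-group blood change as evidence of efficacy or to size the multicenter trial.
6. Reconcile the blank Month 3 blood cell with the sentence saying that initial measures are repeated at Month 3.

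The cost is wording and a short descriptive table; items 1 to 5 need no additional blood draws. The loss is that within-group blood change is no longer an efficacy result.
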